- What is the effect of difelikefalin on CKD-associated pruritus in patients on maintenance hemodialysis?

3.2 Research hypothesis:

- Difelikefalin effectively reduces CKD–associated pruritus in maintenance hemodialysis patients.

4. Objectives

4.1 General objective:

- To evaluate the effect of difelikefalin in CKD-associated pruritus on maintenance hemodialysis patients.

4.2 Specific objectives:

- I. To determine the baseline scores of the WINRS scale and Skindex-10 scale in CKD-associated pruritus on maintenance hemodialysis patients..
- II. To estimate and compare the changes in the WINRS scale, and Skindex-10 Scale between the experimental and control groups.
- III. To assess the tolerability and detect any adverse effect of Difelikefalin in patients with CKD-associated pruritus on maintenance hemodialysis throughout the study period.

5. Materials and method:

5.1. Type of study: Randomized, placebo-controlled, double-blinded trial,

5.2 Place of Study: Department of Nephrology, Chittagong Medical College Hospital, Chattogram, Bangladesh.

5.3 Study period: One and half years from acceptance of protocol.

5.4 Study population: Adult CKD stage-5 patients on MHD in the dialysis unit of the Department of Nephrology, CMCH during the study period.

5.5 Study groups: Based on the interventions, there will be two groups in the study

I. Experimental group:

Standard symptomatic treatment for itching + Intravenous difelikefalin

II. Control group:

Standard symptomatic treatment for itching + Placebo

5.6 Sampling technique: Consecutive sampling. From the Selected participants, the intervention and control will be randomly assigned in a 1:1 ratio (block size of four) through computer-generated randomization.

5.7. Inclusion criteria:

- i. Adults aged ≥ 18 years.
- ii. Patient with chronic kidney disease on HD for ≥ 3 months.
- iii. Moderate-to-severe pruritus (WI-NRS score ≥ 4).
- iv. Able to communicate clearly with the Investigator .
- v. Willing and able to provide written informed consent prior to participating in this study.

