Baseline assessment: CKD patients in HD will be screened consecutively and prospectively by the above inclusion and exclusion criteria to select eligible patients. Eligible patients and their legal relatives will then fully explain the study protocol, their role in the study, and the risks of the study. They will be informed of their right to withdraw from the study at any stage. After getting written informed consent, they will be finally enrolled in the study. Detailed history clinical examination and relevant investigation will be done. Baseline demographic, clinical and biochemical information will be collected from the patients using the case record form and the scales. Blood samples will be collected after an overnight fasting period, with all aseptic precaution 5 mL of venous blood drawn into appropriate vacutainers. iPTH will be measured using a chemiluminescence immunoassay (CLIA). Serum calcium and phosphate will be analyzed using colorimetric methods on a Beckman Coulter AU480 or equivalent validated clinical chemistry analyzer.

Allocation: Once a participant is enrolled in the study and consents to participate, they will be assigned to a treatment group according to the randomization sequence. This assignment will be done immediately after the baseline assessment to ensure that it is truly random. Patients will be randomly assigned to either experimental group or placebo group with a 1:1 allocation. Randomization will be carried out using online software (Research Randomizer Version 4.0 at <https://www.randomizer.org>).

Blinding: The study will be conducted as a double-blind trial, meaning that both the participants and the investigators will be unaware of the treatment assignments.

Interventions:

In the experimental group:

Standard symptomatic treatment for itching + Difelikefalin Dose : 0.5 µg per kilogram of weight after each dialysis session.

Duration: 6 wks

In the control group:

Standard symptomatic treatment for itching + Placebo

Duration: 6 wks

Follow-up:

- i. At the end 3 wks by- WI-NRS scale, Skindex 10 scale & Adverse events
- ii. At the End of 6 wks: WI-NRS scale, Skindex 10 scale & Adverse events

During the 6-week intervention period, patients will report their worst itching intensity using the WI-NRS, and their quality of life will be assessed using the Skindex-10 questionnaire at prespecified follow-up intervals throughout the 6-week period.

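### The adverse-effect grid has no pre-dose reading, so it cannot separate symptoms that dialysis patients already had from new ones; its Withdrawal row is also undefined

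*Protocol*

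**What the plan says.** Protocol section 4.2, objective III, sets out "To assess the tolerability and detect any adverse effect of Difelikefalin in patients with CKD-associated pruritus", "on maintenance hemodialysis throughout the study period".

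The follow-up part of section 5.12 schedules two safety readings:
- "At the end 3 wks by- WI-NRS scale, Skindex 10 scale & Adverse events"
- "At the End of 6 wks: WI-NRS scale, Skindex 10 scale & Adverse events"

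Study drug is given "after each dialysis session", with "Duration: 6 wks" in both groups.

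For baseline, section 5.12 states "Detailed history clinical examination and relevant investigation will be done" and "Baseline demographic, clinical and biochemical information will be collected from the patients using the case record form and the scales". It names no pre-treatment check of the symptoms that are later recorded as adverse effects.

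The case record form in the appendix has two adjacent grids. The WI-NRS and Skindex-10 grid has columns for baseline, week 3 and week 6. The adverse-effect grid is coded no = 0 and yes = 1, with columns for weeks 3 and 6 only. Its rows are nausea, vomiting, dizziness, abdominal pain, muscle spasm, fall, Withdrawal, Expired and others. The form has separate fields for study completion and reason for drop-out.

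**The concern.** Everyone enrolled has had hemodialysis for at least three months (section 5.7), so some may well have nausea, dizziness or muscle spasm before the first dose. A yes at week 3 or week 6 then has two possible meanings: the symptom is new, or it was there all along. The form holds nothing that tells them apart. Because this is a gap in data collection, an analysis plan written later could define a treatment-emergent event but could not recover a pre-dose status that was never recorded.

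Two things are at stake for objective III. The adverse-effect rate reported for each arm may include symptoms that treatment did not cause. The contrast between arms, which is the part that bears on the drug, may also be diluted and less precise.

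A smaller matter is the Withdrawal row. It is undefined, and its two possible meanings call for different handling.

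**Working it through.** **Reading the documents together.** The form contains no pre-treatment symptom reading. Section 5.12 and the form agree on two readings, at weeks 3 and 6. Section 5.11 names the case record form as the data collection instrument, and section 5.13 sends the collected data through a master sheet to SPSS. What the form omits is therefore absent from the stated route to analysis.

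**The plan's own figure.** The illustration uses the planned 51 per arm (section 5.9), which reproduces from the stated inputs:
- [64×36 + 29×71] / 35² × (1.96 + 1.63)² = 45.9, rounded to 46
- 46 × 1.10 = 50.6, rounded to 51

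The point does not rest on this figure.

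**Inputs that are assumptions.** The documents give no symptom prevalence or adverse-event rate. I assume new-onset rates e of 15% (active) and 5% (placebo), and a background prevalence b of 0 to 30%, equal in both arms. I also assume that every background symptom is still present at a reading and is ticked yes.

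**Formulas.**
- Recorded rate = b + (1 − b)e.
- Recorded risk difference = (1 − b)(e_active − e_placebo). It shrinks by (1 − b) and does not change sign.
- Power for recorded rates P and Q with n per arm, two-sided 5%: Φ{[(P − Q) − 1.96√(2p̄(1 − p̄)/n)] / √([P(1 − P) + Q(1 − Q)]/n)}, where p̄ = (P + Q)/2.
- With a baseline reading, new-onset events are compared among the symptom-free, so n becomes 51(1 − b) and the rates are again 15% and 5%.

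**Worked case, b = 20%.**
- Active: 0.20 + 0.80×0.15 = 0.32. Placebo: 0.20 + 0.80×0.05 = 0.24. Difference 0.08 instead of 0.10.
- As written, n = 51 and p̄ = 0.28: (0.08 − 1.96×0.0889)/0.0886 = −1.06, so power is about 14%.
- With baseline, n = 40.8 and p̄ = 0.10: (0.10 − 1.96×0.0664)/0.0655 = −0.46, so power is about 32%.
- About 51 × 0.20 = 10 patients per arm would be recorded yes on account of a background symptom.

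| Background b | Recorded, active vs placebo | Difference (points) | Power as written | Power with baseline reading |
|---|---|---|---|---|
| 0% | 15.0% vs 5.0% | 10 | 39% | 39% |
| 10% | 23.5% vs 14.5% | 9 | 21% | 36% |
| 20% | 32.0% vs 24.0% | 8 | 14% | 32% |
| 30% | 40.5% vs 33.5% | 7 | 11% | 29% |

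With assumed new-onset rates of 20% and 5%, power at b = 10%, 20% and 30% is 38%, 26% and 19% as written, and 59%, 54% and 48% with a baseline reading.

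**The Withdrawal row.**
- For leaving the study: the row stands directly before Expired, and the Data and Safety Monitoring Plan uses withdrawn for leaving the study and has a column for the reason. The form's drop-out section already covers leaving, but death also appears twice on the form, so duplication proves nothing.
- For drug-withdrawal symptoms: the row sits among symptoms, and the reference list includes a paper on opiate-withdrawal rating scales. That paper is not cited in the text and no such scale is scheduled.

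The documents do not settle which is meant.

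**The case against.** The strongest reply is that no rule tells staff to count pre-existing symptoms. The grid is headed as adverse effects, a history and examination are taken at baseline, and the adverse-event log in the Data and Safety Monitoring Plan has columns for onset, end, severity and relatedness. The definition of a treatment-emergent event is commonly left to an analysis plan. This stands to the extent that miscounting is a risk and not a stated rule. It does not close the gap. The log is a monitoring template that nothing links to the form or the master sheet, an onset date exists only once something has been called an adverse event, and the form gives the history no field for these symptoms.

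Second, randomization against placebo gives both arms the same expected background. This stands in full. The harm is limited to inflated rates and dilution. A reader might infer that the gap favours the drug, but a higher recorded rate in the active arm also makes it look worse descriptively.

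Third, the trial is sized on itch response, and even with no background the assumed 15% versus 5% contrast has only 39% power. This stands: a baseline column helps, but does not make the safety comparison well powered.

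A reader might also infer that the schedule cannot detect withdrawal, or guarantees that none is found. The documents do not support this. If the row means leaving the study, the window captures it. If it means drug-withdrawal symptoms, both scheduled readings fall on treatment for patients who complete dosing, but those who stop early could still show them.

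**Conclusion.** The point holds as a cheap improvement to data collection. The adverse-effect grid has no pre-dose reading, the efficacy grid beside it has one, and without it new and pre-existing symptoms cannot be separated on the form that feeds the analysis. The expected consequence is inflated rates in each arm and a risk difference multiplied by (1 − b), with no false difference. At an assumed 15% versus 5% and background of 10 to 30%, power falls to 21–11% as written, against 36–29% with a baseline reading. These sizes are illustrative: they rest on assumed rates, on all 51 per arm being evaluable, and on every background symptom persisting and being ticked. If fewer are ticked, the dilution is smaller.

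The Withdrawal row is ambiguous and needs a definition; nothing stronger follows from it. The absence of a reading after the last dose is not an error either, since section 5.12 confines the scheduled assessments to the six-week intervention period.

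**What to change.** Before enrolment starts:

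1. Add a column headed Baseline (before first dose) to the adverse-effect grid, add the same reading to the baseline assessment in section 5.12, and count as adverse effects only symptoms that are new or worse than baseline. Yes/no boxes can show new but not worse, so worsening needs a short note or simple severity grade in the same cell.
2. Define the Withdrawal row. If it means leaving the study, move it to the drop-out section. If it means drug-withdrawal symptoms, say so, and state that both scheduled readings fall on treatment for patients who complete dosing. Reconcile section 5.12 and the form accordingly.

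The cost is one extra column per patient, completed at an assessment already planned, and one clarified label. No visit or test is added. A reading after the end of treatment could be considered, but it would widen the safety question and lengthen follow-up; it is optional.

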5.8 Exclusion criteria

- i. Known case of Primary skin disease associated with Itching.
- ii. Known case of liver disease.
- iii. Known case of iron deficiency anaemia ,hematological malignancy.
- iv. Known case of hypothyroidism & hyperthyroidism.
- v. Known case of allergic reaction to Opiates .
- vi. Pregnancy.
- vii. Drug abuse, or substance dependence.

5.9. Sample size: Sample size calculation for hypothesis testing of difference between two proportions:

$$n = \frac{p(100 - p) + q(100 - q)}{(p - q)^2} (z_{\alpha} + z_{\beta})^2$$

Where,

Z_{α} = Z value of standard normal distribution at a definite level of significance

Z_{β} = Z value of standard normal distribution at a definite level of power

p = Proportion of patients with expected outcome (response rate) in the experimental group

q = Proportion of patients with expected outcome (response rate) in the control group

Here,

Z_{α} = 1.96 at 95% Confidence Interval

Z_{β} = 1.63 at 95 % power

p = 64% (Fishbane et al., 2020b)

q = 29% (Fishbane et al., 2020b)

So,

$$n = \frac{64(100.0 - 64) + 29(100.0 - 29)}{(64 - 29)^2} (1.96 + 1.63)^2 \approx 46$$

Considering 10% lost to follow-up final sample will be

$$(46 + 46 \times 10\%) \approx 50.6 \approx 51$$

That means 51 patients in each group will be needed in each group to test the hypothesis.

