Safety will be evaluated by monitoring adverse events, vital signs, clinical laboratory measurements in both group.

5.13. Data analysis:

Data will be entered into an Excel sheet to generate the master sheet. After completion of data collection, master sheet will be fed into SPSS (Windows version 27.0) for analysis. This study has two types of data: Categorical and quantitative data. Kolmogorov–Smirnov (K-S) test will be used to determine the data distribution. Finding if there is a significant difference between the data, independent samples t-test (or Mann–Whitney test in case of non-parametric data) and Chi-square test for continuous and categorical data, respectively will be used. The difference between the repeated variable in distinct visits using repeated ANOVA with the change from baseline in the weekly mean WI-NRS scale, Skindex 10 Scale. The adjusted mean difference between the groups and its two-sided 95% CI will be presented. A p -value < 0.05 will be considered significance.

5.14. Expected outcomes: Difelikefalin will significantly reduce pruritus severity compared to placebo. Participants receiving difelikefalin will report improvements in quality of life and will exhibit a favorable safety profile, with no major adverse events.

5.15. The utilization of results: This trial will provide critical evidence on the effectiveness and safety of difelikefalin in a resource-limited setting, addressing a significant unmet need in the management of CKD-aP. If proven effective, difelikefalin could become a standard treatment option for CKDaP and improve the quality of life for hemodialysis patients in Bangladesh and similar populations globally. Efforts will also be made to present these results at conferences and publish them in peer-reviewed national and international journals. The results and observations of the study will be published as a thesis and submitted to the respective university as a part of the requirement for the MD (Nephrology) Phase B examination purpose. The results of the study will be presented to the Department of Nephrology, CMCH.

[figure not shown]

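### Section 5.9 claims 95% power from a z-value and a drop-out step that are both slightly too favourable; with about 46 evaluable per group the chi-square test has about 93%

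*Protocol*

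**What the plan says.** Section 5.9 is introduced as "Sample size calculation for hypothesis testing of difference between two proportions". It takes a response rate of 64% in the experimental group and 29% in the control group, both from an earlier randomised trial of the drug. The two z-values are "1.96 at 95% Confidence Interval" and "1.63 at 95 % power". The formula adds the two separate binomial variances (the unpooled form) and gives about 46 per group.

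The drop-out step is introduced with "Considering 10% lost to follow-up final sample will be". It adds 10% of 46 to 46, giving 50.6, rounded to 51. The section ends: "That means 51 patients in each group will be needed in each group to test the hypothesis". The summary gives the matching total of 102.

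Section 5.13 names a chi-square test for categorical data, with "value < 0.05 will be considered significance" as the criterion and an interval described as "its two-sided 95% CI will be presented". Section 5.10 defines the binary outcome: a fall of at least 3 points in WI-NRS at week 6. The summary leaves open whether the primary analysis is by intention to treat or per protocol.

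**The concern.** Two steps in section 5.9 can be checked from the page, and both are wrong. The z-value printed for 95% power is not the 95% quantile. The allowance for loss multiplies by 1.1 where it should divide by 0.9, so the randomised number, after the loss it is meant to absorb, falls just below the evaluable number it is meant to protect. Both slips lower the sample size.

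The stated power is also not quite the power of the named test at the evaluable number the section plans for. What is at stake is the accuracy of a figure that the thesis and any publication will repeat. The viability of the trial is not in question.

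**Working it through.** **Inputs.** p = 64%, q = 29%, z for alpha = 1.96, z for beta = 1.63, loss 10%, 51 per group (all section 5.9). Two-sided 5% level and chi-square test (section 5.13).

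**1. The protocol's own figure.** n = [p(100 - p) + q(100 - q)] / (p - q)² x (z_alpha + z_beta)².

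- (64 x 36 + 29 x 71) / 35² = (2304 + 2059) / 1225 = 4363 / 1225 = 3.5616.
- 3.5616 x (1.96 + 1.63)² = 3.5616 x 12.888 = 45.90, so 46.
- 46 x 1.1 = 50.6, so 51.

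The printed figures reproduce exactly.

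**2. The z-value.** The standard normal probability below 1.63 is 94.84%; the 95% point is 1.645. Then 3.5616 x (1.96 + 1.645)² = 3.5616 x 12.996 = 46.29, so 47.

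**3. The drop-out step.** 51 x 0.9 = 45.9, below 46. Dividing, 46 / 0.9 = 51.1, so 52. With the z-value also corrected, 47 / 0.9 = 52.2, so 53 per group, or 106 in total against 102.

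**4. Power of the chi-square test at 46 evaluable per group.** The chi-square test uses a pooled variance under the null hypothesis. The mean rate is (0.64 + 0.29) / 2 = 0.465.

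- Null term: sqrt(2 x 0.465 x 0.535) = 0.7054.
- Alternative term: sqrt(0.64 x 0.36 + 0.29 x 0.71) = sqrt(0.4363) = 0.6605.
- Power = Phi[(0.35 x sqrt(46) - 1.96 x 0.7054) / 0.6605] = Phi[(2.3738 - 1.3825) / 0.6605] = Phi(1.501) = 93.3%.
- The protocol's unpooled form at the same n: Phi(2.3738 / 0.6605 - 1.96) = Phi(1.634) = 94.9%.

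Exact enumeration of the two binomial distributions, rejecting when the Pearson statistic exceeds 3.841, gives 92.8%.

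**5. Other readings of who is analysed.** If all 51 are analysed and the 10% lost count as non-responders, the rates become 0.64 x 0.9 = 57.6% and 0.29 x 0.9 = 26.1%. The mean is 0.4185, the null term 0.6977 and the alternative term 0.6611. Power is Phi[(0.315 x sqrt(51) - 1.96 x 0.6977) / 0.6611] = Phi(1.334) = 90.9% by the approximation; enumeration gives 91.7%.

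| Analysed per group | Rates | Chi-square, pooled approximation | Chi-square, exact |
|---|---|---|---|
| 45 | 64% v 29% | 92.8% | 92.1% |
| 46 (51 less 10%) | 64% v 29% | 93.3% | 92.8% |
| 51, drop-outs as non-responders | 57.6% v 26.1% | 90.9% | 91.7% |
| 51, no loss | 64% v 29% | 95.5% | 96.0% |

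**6. Where the gap comes from.** By the protocol's own formula the two slips cost very little power: 94.9% at 46. Most of the distance from 95% to 93% arises because the chi-square test pools the variance under the null hypothesis and the formula does not.

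**The case against.** The strongest reply is that the slips are trivial. Each is worth one patient per group, two when combined (53 v 51), and power stays above 90% on every reading in the table. No decision about the trial changes. This stands, and it is why the point is minor. It does not make the printed z-value or the drop-out step correct.

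A second reply is that the chi-square test is named for categorical data in general and is not tied to the responder outcome, and that the summary describes the primary outcome as a change in score. That conflict is a separate matter. Section 5.9 sizes the trial on two proportions, and chi-square is the only test the protocol names for proportions, so it is the natural reference for the stated power.

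Several stronger readings are tempting but are not supported:

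- **That 51 per group cannot give 95% power.** It does, at 95.5% to 96.0%, if all 51 have a week-6 outcome. The figure of about 93% belongs to about 46 evaluable. The protocol assumes 10% loss but does not settle the analysis set.
- **That the unpooled formula is an error.** It is a standard variant, correctly applied, and gives 94.9% at 46.
- **That power falls to about 89%.** This would need Fisher's exact test or a continuity correction, and section 5.13 names neither.
- **That 102 conflicts with the allocation described in section 5.6 as "randomly assigned in a 1:1 ratio (block size of four").** The last block would be half filled and the groups could differ by at most two. The protocol does not promise exact equality, and power is unaffected.

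**Conclusion.** The point holds as a minor arithmetic correction. The z-value for 95% power should be 1.645, and 10% loss calls for division by 0.9. Each slip is favourable to the design; corrected together under the protocol's own formula they give 53 rather than 51 per group.

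With 51 randomised and about 46 evaluable per group, power for 64% v 29% is about 93%, so the stated 95% is about 2 points too high. The assumptions are the protocol's response rates, the full 10% loss equally in both groups, a two-sided 5% level and an uncorrected chi-square test. Counting drop-outs as non-responders gives about 92%; no loss at all gives about 96%. A reader might infer that the trial is underpowered, but the figures do not support that.

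**What to change.** In section 5.9, print z_beta = 1.645, so that the formula result for 95% power reads 47. Keep 51 per group as the chosen size. Delete the line that adds 10% of 46 to 46 and the closing sentence that presents 51 as the number needed. State the power of the chosen size instead, for example:

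> 51 patients will be randomised to each group. With 10% loss (about 46 evaluable per group), this gives about 93% power for the two-sided 5% chi-square test of 64% v 29%.

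Keeping 51 while putting a division by 0.9 in the derivation would not be consistent, since that yields 52 or 53; this is why the derivation should go. The change costs wording only: no extra patients, and a stated power about 2 points lower.
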